### **3.2.1 Phase I - Baseline**

- Medical history review
- Physical and neurological exam, and neuropsychological tests (see Section 3.2.5)
- Functional Magnetic Resonance Imaging (fMRI)
- Transcranial Magnetic Stimulation (TMS)
- Neurophysiological recordings:
- Electromyography (EMG)/Nerve Conduction Studies (NCS), Electroencephalography (EEG), Quantitative EEG (QEEG), and evoked response assessments involving the Event-related Potential (ERPs) and steady state sensory evoked potentials (SSEP)
- Pre-test the external stimulator prior to implant

### **3.2.2 Phase II - Surgery**

The patient will undergo a standard fronto-parietal image guided craniotomy to expose the sensory and motor cortex. Subsequently, one or two Blackrock Microsystems Neuroport arrays will be implanted into the motor cortex in the standard fashion using the Neuroport pneumatic wand.

The electrodes used in this study are manufactured by Blackrock Microsystems. The Blackrock Microsystems Neuroport array is a 4.4 by 4.2 mm, chronically implantable array containing 96 electrodes, with an electrode spacing of 400  $\mu$ m, capable of recording from areas of the central and peripheral nervous system for extended periods. The electrodes are Parylene-coated, silicon shanks with platinum or iridium oxide tips. The wires connecting the electrode array to the Blackrock connector are 25  $\mu$ m gold alloy insulated wires collectively sealed as a bundle with silicone elastomer. The electrode and wire bundle lengths are user-specified and, once constructed, are not variable. The array of electrodes is biologically inert and can function implanted in cortex for three or more years. The electrodes typically have impedances in the

range of 100-800 kΩ (at 1kHz) and are capable of recording single and multi-unit action potentials with signal-to-noise ratios of up to 10 and peak-to-peak amplitude of greater than 1 mV.

### **Postoperative Management and Monitoring**

Post-operatively, participants will be taken to the neurosurgical step down unit and subsequently to the routine patient ward. Participants will also have a CT scan post operatively to evaluate the brain for intracranial air, hemorrhage and to assess the location of the electrodes.

### **Surgical recovery**

Following surgery, participants will return to their home and enter into a postoperative recovery phase, which is normally expected to be 1-2 weeks from the initial implant, but may take longer depending on wound healing time. The pedestal site should be cleaned at least once every seven days or as required. This procedure will most likely require some assistance from a caregiver. To help reduce the risk of infection, it is important that all caregivers who touch the patient above the neck have clipped nails. The Pedestal Cap should remain on the Pedestal at all times and should only be removed by the physicians or trained investigators on the study. Caregivers should be careful not to touch the pedestal without first touching the patient elsewhere (skin to skin) to discharge any static electricity, and not to bump the Pedestal Connector.

#### **3.2.3 Phase III - Decoding and Stimulation**

Neural signals from the implant will be monitored and re-coded by the Neural Bridging System. Re-coding involves the process of decoding neural signals and then encoding the appropriate stimulation patterns for an intended movement. Decoding algorithms will decipher neural signals using pattern recognition methods to classify different movements imagined by the participant. The Battelle Neuromuscular stimulator will be setup and calibrated to evoke the imagined wrist and hand/finger movements. Encoding algorithms will use the calibration data and the decoded data to create the appropriate spatial and temporal stimulation patterns to evoke imagined movements.

Each subject will be asked to participate in test sessions, for up to 3 times a week for about 60 months. Each session will typically last less than 4 hours (including setup time). The first 30 minutes, approximately, will be needed for setup of the Blackrock and stimulator system. Once the stimulator is calibrated, the participant will be asked to imagine wrist and hand movements and the decoding algorithms will identify the desired movements. Once a select set of imagined movements have been identified, the stimulator system will apply the appropriate spatial stimulation patterns to the forearm to achieve motion in the paralyzed limb. This will give the patient voluntary control of the select movements in the paralyzed limb. Neurophysiological recordings and evaluations will also be conducted during these test sessions. Active stimulation time will be monitored to avoid fatigue. Trained study personnel will set up and perform the device during the study visits. At the conclusion of the study, the patients will have the cortical implant removed via a second procedure.

The participant(s) will receive haptic feedback above the level of their injury during motor tasks to enhance their motor performance. Haptic feedback simply provides a skin sensation (e.g. vibration), is well characterized in the literature (Shull & Damian, 2015), and is a well-studied and safe stimulus carrying no significant increase in risk. The apparatus will be electrically isolated from the participant. The participants currently receive electrical skin stimulation for feedback in the study. Haptic feedback is a non-electrical safer means of providing even more meaningful sensory information to enhance motor capability.

During this phase of the study a virtual reality headset may be used to provide visualizations of imagined movements. If the virtual reality headset is not used, the virtual environment will be displayed on a screen. On occasion, the virtual reality headset may show the participant incongruent movements, that is, movements different from reality, to study the participant's sense of agency. This reanimation study offers a unique opportunity to study the neural mechanisms of motor awareness, such as sense of agency or movement intentions. Agency is the sense that we control the actions of our own body (Gallagher, 2000; Jeannerod, 2003) and is a fundamental aspect of the experience of self. In this study, normal efferent and afferent sensorimotor information is replaced by the reanimation system and visual feedback, respectively. Congruent and incongruent visual feedback presented via virtual reality may

provide important information about the fundamental mechanisms of self-awareness. The importance of showing both congruent (the VR representation looks the same as the intended movement) and incongruent (the VR representation shows different movement than the participant's intended movement, is important in understanding whether or not the participant is self-aware of the movements he is making with his paralyzed limb. This type of VR experiment is currently being done with the participant (i.e. showing congruent and incongruent movements), but on a flat screen which is a less immersive and less engaging environment. The addition of the device may remove some bias of the participant being able to see his limb, which is typically covered to some degree, but is never completely out of view.

Use of VR will advance our current “screen-limited” understanding of the reasons that influence ownership or control a person with tetraplegia may have over a hand or limb they cannot feel. It is anticipated that improving visualization and subjective feeling of movement during training will enhance training efficiency and make it easier for participants to move their limbs. We will explore whether brain-computer interface training using virtual reality decreases training time compared to standard (non-VR) training protocols.

A brain machine interface is expected to function at all times, interpreting brain activity and producing movements. One way our brain limits the production of activity from neural activity in the motor cortex is by gating the signal emanating from motor cortex during various state of consciousness. Therefore the brain machine interface should be able to understand different brain states and adjust its function appropriately. Currently we have very limited knowledge about the activity of motor cortex during sleep in primates. Some have suggested that the activity of neurons during certain parts of the sleep cycle may be related to motor learning. EEG/EMG recordings and intracortical data from our participants will allow us to better understand the relationship between brain activity and motor output during various stages of sleep.

Additional to the weekly test sessions, the participant will be admitted to The Ohio State Wexner Medical Center for overnight sleep evaluations. We will ask the participant to perform a variety of motor tasks. Those will be similar to the ones that the participant performed during the recording sessions. While the participant is performing the motor tasks we will record EMG

from biceps, triceps, and deltoids along with recording the EEG and intracortical activity. We will continuously record this activity throughout the night in order to correlate it with various sleep stages.

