#### **4.4 Study Justification**

The target population will be people with C4-6 ASIA A spinal cord injuries (motor and sensory complete neurologic injuries ) who are more than 1 year post injury and who are neurologically stable. This population has no potential for additional neurological recovery of functional movement. People with this level of paralysis are totally dependent in all aspects of self-care. Restoration of functional movement in this population requires exploration of neuroprosthetic applications to increase functional movement that has quality of life implications. This BCI system is the first attempt to utilize cortical sensors and a high resolution stimulation system to bypass the injured spinal cord and produce volitional movement in humans.

The sleeve configuration of the NMES represents an incremental step toward portability for the system. The sleeve provides a less operator-dependent, more convenient application and removal of the electrode cuff. The electrodes and circuitry are otherwise identical to the cuff.

This reanimation study offers a unique opportunity to study the neural mechanisms of motor awareness, such as sense of agency or movement intentions. Agency is the sense that we control the actions of our own body (Gallagher, 2000; Jeannerod, 2003) and is a fundamental aspect of the experience of self. In this study, normal efferent and afferent sensorimotor information is replaced by the reanimation system and visual feedback, respectively. Congruent and incongruent visual feedback presented via virtual reality may provide important information about the fundamental mechanisms of self-awareness. This is clinically relevant to developing neuroprosthetics that maximize user acceptance by enhancing integration with the users' body image. In addition, we will study whether using virtual reality (VR) can provide a more efficient way to train motor cortex neural decoders.

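### Agency experiment: the protocol calls the participant's view of his real limb a bias, but does not require the limb to be hidden in agency blocks

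*Combined protocol and SAP*

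**What the plan says.** All of this is in the combined protocol and SAP, mainly Section 3.2.3 (Phase III).

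- **Display.** The headset is optional: "a virtual reality headset may be used to provide visualizations of imagined movements". The fallback follows at once: "If the virtual reality headset is not used, the virtual environment will be displayed on a screen".
- **Incongruent trials.** "On occasion, the virtual reality headset may show the participant incongruent movements, that is, movements different from reality". The stated purpose is to study sense of agency. Later in the same section, incongruent is described instead as a display that differs from the movement the participant intended.
- **Current practice.** The experiment is said to be running already, "i.e. showing congruent and incongruent movements), but on a flat screen which is a less immersive and less engaging environment".
- **The acknowledged bias.** The headset is offered as a partial remedy: "The addition of the device may remove some bias of the participant". The source of that bias is then given as his "being able to see his limb, which is typically covered to some degree, but is never completely out of view".
- **Rationale.** Sections 3.2.3 and 4.4 both say that "normal efferent and afferent sensorimotor information is replaced by the reanimation system and visual feedback, respectively".
- **Other feedback.** "The participant(s) will receive haptic feedback above the level of their injury during motor tasks to enhance their motor performance". The section adds that electrical stimulation of the skin is already used for feedback.

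Section 3.3 names voluntary movement as the primary outcome and functional movement as the secondary. It defines no agency measure or analysis.

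**The concern.** The agency experiment alters what the participant sees of his movement and observes how he responds. If he can also see the real hand, he has a second source of information that the display does not control. On an incongruent trial the hand contradicts the display; on a congruent trial it agrees. The leak therefore works differently in the two trial types, and it falls on the contrast the experiment is meant to measure.

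A response that disowns the displayed movement could then mean altered agency, or simply that the participant compared the screen with his hand. More trials would not separate the two explanations, because the problem is bias and not noise. The protocol identifies this weakness and offers a partial remedy, but still permits the arrangement that causes it.

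What is at stake is whether an exploratory result can be interpreted. Section 4.4 gives the study of agency as part of the justification for the work, and Section 4.1 lists participant risks from the headset and from incongruent displays. The data collected at that burden should be able to answer the question.

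**Working it through.** The plan states no figure on this point, so there is none to reproduce. The check is a comparison of the relevant statements, followed by an illustration on assumed inputs.

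**Step 1. Is the limb visible?** On the flat screen, yes in part: Section 3.2.3 says it is covered to a degree but never wholly hidden. With the headset, the section claims only that some of the bias may be removed.

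**Step 2. Does the plan confine agency trials to the headset?** No. The sentence introducing incongruent displays names the headset, but headset use is optional, the screen is the general substitute, and the same experiment is already run on a screen. No section restricts agency blocks to the headset or requires full occlusion.

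**Step 3. Does visibility reveal the manipulation?** This depends on the definition of incongruent.

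- *Different from reality:* yes. Sight of the real limb is direct evidence of the mismatch.
- *Different from the intended movement:* less clearly. The participant knows what he intended, so he could detect this mismatch with the limb hidden.

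The two definitions coincide only when the stimulated limb does what the participant intended. When it does not, a display can match the intention and still differ from reality, and the section does not say how such a trial is classed.

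**Step 4. Is there a second leak through the skin?** Haptic feedback is given above the injury, where it can be felt, during motor tasks. The section does not say whether the signal follows the actual, displayed or decoded movement, or whether it is on in agency blocks. If it follows the actual movement, it could reveal the mismatch. If it follows the display, it could support the illusion. If it follows decoded intent, it need not differ between trial types. The documents do not say which applies.

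**Step 5. Illustration.** Let *r* be the proportion of incongruent trials on which a fully masked participant rejects agency, and *d* the proportion on which he detects the true movement. Assume that detection always leads to rejection. Then

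observed rejection = *d* × 1 + (1 − *d*) × *r*, and the excess over *r* is *d* × (1 − *r*).

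Both inputs are assumptions: *r* = 0.30, with *d* varied.

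| *d* | Observed rejection | Excess over *r* |
|---|---|---|
| 0 | 0 + 1 × 0.30 = 30% | 0 points |
| 0.25 | 0.25 + 0.75 × 0.30 = 47.5% | 17.5 points |
| 0.50 | 0.50 + 0.50 × 0.30 = 65% | 35 points |

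The documents describe no such response scale. The table shows direction and how the excess grows with detection; it does not estimate the bias in this study.

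**The case against.** The strongest reply is that the protocol discloses the problem and adds the headset partly to address it, and that the one forward-looking sentence on incongruent displays names the headset. On that reading the flat-screen version is existing practice that is being replaced. This has some force: future agency trials on the screen are not excluded, but neither are they announced. It does not remove the defect, because headset use is optional, the screen fallback has no exception for agency trials, and the headset is credited with removing only some of the bias.

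A second reply is that agency is exploratory. That stands. It is neither a primary nor a secondary outcome in Section 3.3. Section 3.1 enrols up to 5 participants, and Section 4.5 describes a proof-of-concept study that will not support a regulatory submission.

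A third reply is that awareness of the true movement may be part of the question, since Section 3.2.3 also asks whether the participant is aware of what his paralysed limb is doing. This stands in part. It is a reason to fix the definition of incongruent; it does not justify leaving the limb in view without saying so.

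A reader might also infer three stronger points that the documents do not support:

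- *That haptic feedback breaks the masking.* What it encodes, and whether it is on in agency blocks, is not stated.
- *That Section 4.4 makes vision the participant's only source of information a condition of validity.* It says that visual feedback replaces normal afferent information. It does not say that nothing else reaches him.
- *That a planned screen-versus-headset comparison of agency is biased.* None is planned, and no pooling of the two is proposed. The stated comparison of VR with non-VR training concerns training time.

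**Conclusion.** The concern holds in a limited form. The plan permits the agency experiment to run with the real limb partly in view, after naming this as a bias, and sets no requirement that would prevent it. Where incongruent means different from reality, responses on such trials may reflect sight of the true movement, and the planned descriptive summaries cannot separate that from altered agency.

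The size cannot be derived from the documents. The 47.5% and 65% figures rest wholly on the assumed *r*, the assumed *d*, and the assumption that detection always leads to rejection.

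The conclusion rests on two further assumptions: that some agency blocks are or will be run on the screen, which the text permits and current practice supports, and that the reality-based definition of incongruent applies. Under the intention-based definition the argument is weaker.

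A reader might take this as a threat to the trial's main result. It is not: neither the primary nor the secondary outcome depends on the agency experiment. The feedback through the skin is an unstated detail that calls for a precaution, not a demonstrated source of bias.

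**What to change.** Add one paragraph to Section 3.2.3 covering all agency blocks, congruent and incongruent:

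1. **Occlusion.** The limb is fully outside the participant's line of sight, by headset or by an opaque partition on his side. Set the requirement on what he can see, not on the device, since the protocol credits the headset with only partial removal of the bias. The partition must leave the investigator able to watch the sleeve and skin, as Section 4.1 requires.
2. **Data with the limb in view.** Report any such agency data separately, including flat-screen data already collected.
3. **Definition.** Use one meaning of incongruent, either different from the actual movement or different from the intended one, and state how trials are classed when the limb does not do what was intended.
4. **Precaution on felt feedback.** State what the haptic and electrical skin feedback encodes. In agency blocks keep it off, or deliver it identically in congruent and incongruent trials.

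The cost is minor setup work (a partition and a feedback setting) within sessions already planned, plus the protocol text. The main drawback is that earlier flat-screen agency data will carry less weight.

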### **3.2.4 Phase IV - Follow-up**

The subject will have the device explanted when the study team and Principal Investigator have determined the subject is healthy enough to undergo explantation. After explantation surgery, participants will be asked to complete the same fMRI, neurophysiological recordings, neuropsychological tests, and TMS procedures as they did during the baseline phase.

### **3.2.5 Study Specific Procedures**

#### **Neuropsychological Tests**

Neuropsychological tests are useful to us to help categorize whether there are minimum neuropsychological criteria for successful patient selection and to determine safety (i.e., whether the procedure carries risk of decline in neuropsychological function post-explant).

Neuropsychological tests will include but not limited to:

- Motor-Free Visual Perception Test (MVPT-3)
- Wechsler Adult Intelligence Scale (WAIS-III)
- Wechsler Memory Scale (WMS-III)
- Delis – Kaplan Executive Function System (DKEFS)

#### **Neurophysiological Recordings**

The neurophysiological recording and evaluations will include Electromyography (EMG)/Nerve Conduction Studies (NCS), Electroencephalography (EEG) EEG, Quantitative EEG (QEEG), and evoked response assessments involving the Event-related Potential (ERPs) and steady state sensory evoked potentials (SSEP). These studies are non-invasive and are routinely performed in the hospital and the clinic by the Ohio State Neurophysiology, PM&R and epilepsy teams. These studies will be performed at various times and will involve spontaneous recordings as well as recordings linked to decision making paradigms as well as auditory, tactile and visual non-

invasive stimuli. These evaluations may also be performed in conjunction with intraoperative microelectrode recording and stimulation.

Electroencephalography (EEG) is a routine physiological measure of cerebral function that has been used to evaluate TBI as well as to prognosticate survival and global outcome after TBI. Quantitative EEG (QEEG) methods evaluate brain functions and task specific EEG changes that can provide information about patterns of brain activity related to attention, learning and behavior. QEEG results in the same patient before and following cortical array implantation will allow changes in brain function to be quantified. Event-related potentials (ERPs) reflect processing that involves selective attention, memory, comprehension and other types of cognitive activity in the brain. ERP provides a non-invasive method of studying cognitive processes in both normal and pathological states. Comparing recordings before, during, and following cortical array implantation will allow changes in cognitive activity to be quantified. P300 is an ERP elicited by visual stimuli. The characteristics of the P300 have been used as metrics of cognitive function. Steady state evoked potentials to periodic stimuli and somatosensory evoked potentials can be used to quantify and characterize the strength of sensory signals that reach the brain for processing. This information is critical for phenotyping the degree of disruption of sensory tract inflow of spinal cord injured patients, evaluating the somatosensory contribution to motor ERPs and intracortical motor unit activity, and determining whether plasticity changes sensory tract inflow between pre- and post-implant conditions.

Electromyography (EMG) and nerve conduction studies (NCS) evaluate peripheral sensory and motor nerve pathway integrity, which can be lost to different degrees by patients with different levels and severity of spinal cord injury. EMG of the patient's limbs will be collected pre- and post-implant and during decoding/stimulation to quantify and characterize the strength of voluntary motor signals that reach limb muscles. This information is critical for phenotyping the degree of disruption of motor tract outflow of spinal cord injured patients, evaluating voluntary vs. brain-machine interface stimulated motor patterns that can be elicited, and determining whether study participation is associated with plasticity changes in motor tract outflow from brain through the spinal cord. Nerve conduction studies (NCS) will be collected pre and post-

implant to characterize the integrity of peripheral sensory and motor pathways, which further helps to phenotype patients with spinal cord injury.

